9.1 Specimen Collection and Banking for Future Use

As described previously, biospecimens (urine, saliva) will be collected after obtaining written informed consent at the Pre-Challenge Visit and Stress Exposure Visit and these biospecimens will be stored at the Research Nexus Laboratory at MUSC to complete procedures related to determining eligibility (Pre-Challenge Visit) and evaluating stress responses (Stress Exposure Visit). Saliva samples will also be obtained at home following the Stress Exposure Visit; these biospecimens will be processed and stored at the Research Nexus Laboratory until statistical analyses have been completed. Once statistical analyses have been completed, biospecimens will be stored in the Nexus Laboratory until the end of the project period. All biospecimens will be stored in the Nexus Laboratory using a unique numeric identification

number to link samples with participants. Further, all biospecimens will be coded with a numeric identifier to link test results with (e.g., changes in cortisol, cotinine levels) with subject data obtained during the screening and baseline telephone interview and clinical data (e.g., co-morbidities) abstracted from electronic health records. All linked subject data will be de-identified and stored in a secured, password-protected database at MUSC using their identification number.

Participants also have the option to provide written informed consent for biospecimens to be included in the TRACER Biorepository. The TRACER biorepository is located at VCU; biospecimens from this study will be shipped to the TRACER biorepository using standard shipping procedures. The Project Manager for this study will work with Nexus staff to ensure that samples are sent to the TRACER Biorepository and to document receipt of biospecimens. Additionally, de-identified participant-level data will be uploaded into a centralized database at the TRACER Biorepository. Access to biospecimens, test results, and linked data will be limited to study investigators, research staff within the scope of their roles (e.g., Project Manager), and investigators in the TRACER Biorepository.

9.2 Specimen/Banking for Future Use

The TRACER Biorepository will bank biospecimens in the facility located at VCU and de-identified participant data (e.g., race, age, zip code, self-reported data on income, education, etc., and census level information on social determinants of health) that are linked with these biospecimens will be stored on a centralized, secure database in the TRACER Biorepository. This information will be stored in the TRACER Biorepository until the end of the project period. At the end of TRACER, samples and de-identified participant data will be destroyed. Participants can request that their biospecimen/data be withdrawn from the TRACER Biorepository by submitting a Withdrawal of Informed Consent for Use of Specimens to the study project manager. Once this request is received, biospecimens and data will be destroyed or removed from the TRACER Biorepository.

Biospecimens and participant data collected as part of this study will be used in future research that is conducted by TRACER investigators and may include genomic/genetic analyses. A standard process will be used to release biospecimens and data to TRACER investigators. Specifically, TRACER investigators will submit a written Request for Samples. The Request for Samples will describe the type of samples needed, the purpose of the study, and documentation of IRB approval or exempt from human subjects designation. The Request for Samples will be reviewed by investigators in the TRACER Biorepository with a recommendation to approve or deny the request for samples. The TRACER Executive Council will make final decisions about approving or denying the request for samples. Only de-identified biospecimens and/or data will be released to TRACER investigators. A Material Transfer Agreement/Data Transfer Agreement (MTA/DAT) will be established by TRACER institutions prior to inter-institutional data sharing and transfer of biospecimens and data.

10. Data Management

10.1 Statistical Considerations and Sample Size Justification by Specific Aim. This section describes the sample size and power estimates for the study and also describes the statistical analyses that will be completed to address the specific aims for the study.

Aim 1: Examine racial differences in acute physiological stress responses between AA/Black and white male smokers using a laboratory model. The association between acute physiological stress response and tobacco-related behaviors will also be evaluated. *Hypotheses:* AA/Black smokers will be more likely than white smokers to have a blunted cortisol response to an acute laboratory stressor. AA/Black smokers will have lower absolute cortisol values during the acute stressor compared to white smokers. AA/Black smokers will have significantly greater cigarette craving and be more likely to smoke following exposure to an acute physiological stressor compared to white smokers following an acute laboratory stressor.

Sample Size and Power Calculations: This aim will examine racial disparities in cortisol responses to an acute stressor among AA/Black and white male smokers in a laboratory setting. Changes in cortisol levels will be the primary outcome variable and will be measured multiple times during the course of the TSST. A sample size of 50 AA/Black (Mean DCS=0.20, SD=0.20) and 50 white (Mean DCS=0.35, SD=0.30) males achieves 84% power to detect a difference of 0.15 μ g/dL between the 2 groups with a significance level of 0.05 using a two-sided two-sample *t*-test. This sample size would also provide 80% power to detect a difference of 0.14 μ g/dL in absolute cortisol value between AA/Black (mean=0.17, SD=0.19) and white (mean=0.31, SD=0.30) males with a significance level of 0.05 using a two-sided two-sample *t*-test.

Statistical Analysis: First, descriptive statistics will be generated to characterize enrollment outcomes using clinical data (e.g., co-morbidities, age, etc) obtained from the EHR during the recruitment process. Statistical analyses will compare enrollees vs. decliners in terms of race, clinical factors, and smoking history to identify variables that should be controlled for in the analysis of stress reactivity and smoking behaviors.

To examine the effects of race on acute stress responses to the TSST laboratory stressor the response area under the curve (rAUC) for cortisol will be calculated using trapezoidal approximation with the samples obtained at time zero (T0) to the last measurement (T24m). Analysis will adjust for baseline cortisol levels by subtracting the rectangle defined the baseline sample and total observation time (T24min) from the total area under the curve, thus, it is possible to have negative rAUC values if cortisol levels decline below baseline.⁹¹ A generalized linear regression model will be conducted with rAUC as the dependent variable and race (AA/Black, white) as the between-subjects factor. The effects of nicotine metabolism rates, nicotine dependence, and cigarettes smoked per day will be examined in analysis of covariance that include rAUC as the dependent variable and race as the between-subjects variable. The extent to which cortisol changes are blunted will be determined by calculating the difference between the first and last cortisol assessment during the TSST.⁹⁰ Cortisol values that do not change over time or those that are closer to zero will be considered blunted.³⁰ Similar regression models will be used to test for racial differences in cortisol levels at each timepoint following exposure to an acute laboratory stressor, the proportion who smoke after the TSST, and scores for cigarette craving. A random effect will be added to the statistical models to allow for differences in participants recruited from different sites (MUSC and VCU). Models will be adjusted for known and potential confounders (e.g., nicotine metabolism rates).

Aim 2. Evaluate racial differences in *daily* cortisol patterns between AA/Black and white male smokers. *Hypotheses:* AA/Black smokers will be more likely than white smokers to have blunted daily DCS. Compared to white smokers, AA/Black smokers will have lower absolute cortisol values during the waking day. This aim will examine racial disparities in cortisol responses between AA/Black and white male smokers in their neighborhood and community settings at 4- and 8-weeks after the TSST has been completed. Changes in cortisol levels will be the primary outcome variable and will be measured at multiple critical timepoints during the waking day.

Sample Size and Power Calculations: A sample size of 50 AA/Black (Mean DCS=0.12, SD=0.15) and 50 white (Mean DCS=0.26, SD=0.30) males achieves 84% power to detect a difference of 0.14 μ g/dL between the 2 groups with a significance level of 0.05 using a two-sided two-sample *t*-test, assuming similar differences between the groups at 4 and at 8 weeks of follow-up. This sample size would also provide 83% power to detect a difference of 0.13 μ g/dL in absolute cortisol value between AA/Black (mean=0.35, SD=0.19) and white (mean=0.48, SD=0.35) males with a significance level of 0.05 using a two-sided two-sample *t*-test.

Statistical Analysis: A similar approach to Specific Aim 1 will be used to examine racial differences in daily cortisol levels. Racial differences in mean cortisol levels at 4 weeks will be modeled by a generalized linear model similar to Specific Aim 1 with the addition of a repeated statement to account for the multiple measures taken for each participant throughout the day and a random intercept to allow for individual differences. The same will be done at 8 weeks post TSST. Models will include race and time-of-day as fixed effects and the interaction between them. Model-based contrasts will be used to conduct group

comparisons based on the fitted model. Blunted cortisol DCS will be defined similarly as in Specific Aim 1. Generalized linear models will be used to examine racial differences in blunted DCS at each post-TSST assessment. Similar models will examine the relationship between blunted DCS (at 4 and 8 weeks post-TSST) and baseline measures of smoking behavior (e.g., smoking history, nicotine dependence, nicotine metabolism rates), and stressors (chronic SES stressors, psychosocial stressors, and structural stressors).

Aim 3: Identify factors that are important to acute and daily stress responses among AA/Black and white male smokers by examining acute and daily cortisol patterns based on exposure to chronic stressors. *Hypotheses:* Acute and daily cortisol responses will be associated with chronic stressors such that men who have greater exposure to SES, structural, and psychosocial stressors will have blunted acute and daily cortisol patterns. The relationship between acute and daily cortisol patterns, nicotine metabolism, and nicotine dependence will also be explored.

Sample Size and Power Calculations: It is hypothesized that men who have a higher nicotine addiction (daily versus non-daily or higher FTND score versus lower) will have higher cortisol levels. A sample size of 100 males achieves 82% power to detect a ratio of 1.25 (25% higher cortisol levels among the highly addicted) when the ratio under the null hypothesis is 1 and the coefficient of variation on the original scale is 0.4 with a significance level of 0.05 using a two-sided two-sample *t*-test.

Statistical Analysis: Similar to Specific Aims 1 and 2, Specific Aim 3 multivariable generalized linear regression models will be used to identify factors that are important to acute (baseline) and daily (4 and 8 weeks post-TSST) stress responses (cortisol patterns). Independent associations between blunted cortisol responses and race, smoking behaviors, nicotine dependence at baseline, SES, and psychosocial and structural stressors will be evaluated.

10.2 Data Storage and Privacy Protection. The data management system for the study will be designed to achieve the major elements of the study including: (1) determination of study eligibility, (2) monitoring recruitment and accrual, (3) generation of study materials, and (4) storage of data from telephone interviews and laboratory assessments. All data collected as part of this study will be stored on a MUSC-based secure password-protected network server. Moreover, access to the server will be monitored by the PI and limited to pertinent study personnel.

We will take extensive precautions to protect the privacy of the participants. Personal health identifiers (e.g., name, address) will not be used to identify participants in study databases or on laboratory materials. We will use a confidential subject identification number to identify all participant data in research databases and on study documents (e.g., baseline telephone assessments), and laboratory materials (i.e. clinic flow sheets, biospecimen tubes). Cortisol saliva kits and other biospecimen collection tubes will be labeled with the study identification number. A key containing each participant's name, study identification number, and telephone number will be kept on a secure, password-protected database on a MUSC network server until study procedures have been completed and the data have been checked for completeness and accuracy. At that time, this identifying information will be destroyed. Thus, we will retain no identifying information in the study data files. Moreover, all computerized study databases for clinical and questionnaire data will be housed on a secure, password-protected network server. All personal contact information will be kept in a database that will be housed separately from the database containing questionnaire data. There will be limited access to study files and study databases throughout the duration of the study; only pertinent study staff will have access to study information.

All MUSC data including biospecimens, social determinants of health, clinical data, and sociodemographic data will be de-identified before being sent to the TRACER VCU centralized database that will be the repository for all TRACER-affiliated projects. The centralized database will ensure data harmonization, uniformity, quality control and privacy. VCU TRACER investigators will be responsible for abiding to HIPPA

compliance, and compliance with federal and local regulations. Data will be collected in REDCap instruments to facilitate data integration into the centralized database.

Handling Incidental Findings and Adverse Effects. In the event of any unexpected events related to incidental findings, safety concerns, and adverse effects, the PIs and/or study staff will contact the MUSC and VCU IRBs to discuss appropriate action.

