TSST Stress Exposure Visit. The stress exposure visit will be completed within 72-hours of completing the pre-challenge visit. As with the pre-challenge visit, participants will be instructed to smoke as usual, but not to eat or drink during 1-hour prior to stress exposure visit. The number and brand of cigarettes smoked prior to the TSST will be recorded. Participants will be asked to smoke a single cigarette of their usual brand prior to initiating the stress test to standardize the time since last smoking. Fifteen minutes later, baseline clinical and subjective measures will be obtained. Clinical measurements will include heart rate and blood pressure using a standardized monitor, and saliva collection using a Salivette. Following collection of these baseline measures, participants will be escorted back to their room to start the TSST. The TSST is a standardized psychological stress challenge that has been validated and used extensively in research studies; a meta-analysis supports that it is the gold standard for evoking an HPA-axis stress response in a laboratory setting. The TSST (see **TSST Procedures and Timeline**) will be administered in

the Research Nexus Lab. Outcome measures (e.g., cortisol responses) will be collected prospectively during the stress exposure visit. Heart rate variability (HRV) and blood pressure will also be measured using standard medical equipment and procedures during the TSST. Cigarette craving and smoking behavior will be measured after the TSST has been completed. Specifically, smokers will rate their urge to smoke immediately after the last saliva sample has been taken as part of the TSST. After completing this self-report measure, they will be given the opportunity to smoke a cigarette using a pocket CReSS system that measures and records smoking topography (Puff #, Volume, IPI). Smoking behavior (smoke versus not smoke) will be recorded in the participant's study chart and stored in study's data management Redcap system.

TSST Procedures and Timeline		
TIME	EXPERIMENTAL PROCEDURE	STRESS ASSESSMENT
3:00pm	Acclimation period (15 minute duration)	Patient arrives and given relaxation tools (i.e. spa video, magazine, nature scenes)
Baseline (immediately following acclimation period)	Stress measurements	Take cortisol, BP, HR, and assess SUD
Immediately before TSST (12 minutes following baseline)	Stress measurements	Take cortisol, BP, HR, assess SUD, and explain the task and give participant paper to write notes

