3:33- 3:44	TSST	
5	Interview task	
5	Arithmetic task	
Post TSST stress assessments (12 minute increments)		
Post TSST (2 minutes following TSST)	Post-TSST Assessment	Cortisol, BP, HR, SUD
12 mins post TSST	Post-TSST Assessment	Cortisol, BP, HR, SUD
24 mins post TSST	Final Post-TSST Assessment	Cortisol, BP, HR, SUD

Post-Stress Test Saliva Collection. At the end of the TSST, participants will be given saliva kits (Salimetrics oral swab) to collect samples at home 4- and 8-weeks after the stress exposure visit. Self-reported data on perceived stress and life experiences during the past month will also be obtained using validated instruments. Standard collection procedures (e.g., avoid eating/drinking/brushing teeth within 1-hour of sample collection; do not engage in vigorous physical activity; no alcohol within 12-hours of sample collection) will be provided to participants as an instructional sheet. Saliva will be collected at fixed intervals (upon waking, 30-minutes after waking, 4:00 pm, and 6:30 pm). The final 6:30pm saliva collection will occur at the Nexus Laboratory and participants will be instructed to return their other collected samples from home at this time. Collection dates will be based on the date the stress exposure visit was completed and sample collection procedures will be explained verbally and in writing at the end of the stress exposure visit. Participants will be given an instructional sheet for how to perform the sample collections. Participants will also be given a collection log to record the date and time of each collection, the number and brand of cigarettes smoked on the collection day, quit attempts, the amount of stress experienced during the past month, and positive and negative life experiences during the past month. Participants will be contacted the night before the collection date by telephone, email, and text to remind them about the sample collection date, collection and storage procedures, and the information that should be recorded in the sample collection log. Saliva samples will be collected at 4- and 8-weeks after the TSST to be consistent with the collection timepoints used in previous research with African American and white treatment-seeking smokers.

9.0 Data Collection and Storage.

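### Does the T24min label leave baseline cortisol inside the Aim 1 rAUC?

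*Combined protocol and SAP*

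**What the plan says.** Section 10.1, Aim 1, Statistical Analysis, computes rAUC by the trapezoidal rule from the "samples obtained at time zero (T0) to the last measurement (T24m"). Baseline is then removed "by subtracting the rectangle defined the baseline sample and total observation time (T24min) from the total area under the curve". The plan adds that "it is possible to have negative rAUC values if cortisol levels decline below baseline". rAUC is the dependent variable in the model for race and in the covariance analyses with the nicotine variables. Blunting is defined separately, by "calculating the difference between the first and last cortisol assessment during the TSST".

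The TSST Procedures and Timeline table in Section 8.0 schedules five cortisol samples. Two precede the stressor: "Baseline (immediately following acclimation period") and "Immediately before TSST (12 minutes following baseline"). The other three come under the heading "Post TSST stress assessments (12 minute increments"): "Post TSST (2 minutes following TSST"), then 12 and 24 minutes after the TSST. Section 10.1 does not say which of these samples is T0.

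**The concern.** A baseline-corrected area is free of baseline level only if the subtracted rectangle is as wide as the curve. The plan prints T24min beside the width, yet no scheduled sample lies 24 minutes before the last one. The 24 minutes run from the end of the TSST, when no saliva is taken.

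An analyst who took the parenthesis as a duration, and started the curve at the Baseline row, would subtract too small a rectangle. Part of each man's baseline cortisol would remain in his response score. If African American and white smokers differed in baseline cortisol, the race comparison of rAUC would pick up that difference even with identical stress responses. If baseline were lower in African American smokers, the artefact would run in the direction of the blunting hypothesis. The rectangle is the only adjustment for baseline cortisol that the plan describes.

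**Working it through.** **Inputs.** From the Section 8.0 timeline: start 3:00, acclimation 15 minutes, second sample 12 minutes after baseline, TSST 3:33 to 3:44 (two tasks of 5 minutes), and post-TSST samples at 2, 12 and 24 minutes. From the Section 10.1 Aim 1 power paragraph: absolute cortisol means of 0.17 and 0.31 μg/dL. Using these as baseline values is an assumption made only to give a scale.

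**Sample times.** Baseline is 3:00 + 15 = 3:15. The pre-TSST sample is 3:15 + 12 = 3:27. The later samples are 3:46, 3:56 and 4:08.

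| Curve starts at | Clock times | Stated intervals only |
|---|---|---|
| Baseline | 4:08 − 3:15 = 53 min | 12 + 10 + 24 = 46 min |
| Pre-TSST sample | 4:08 − 3:27 = 41 min | 10 + 24 = 34 min |
| First post-TSST sample | 24 − 2 = 22 min | 22 min |

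**Residual.** Let S be the span of the curve, W the width of the rectangle and C0 the baseline value. A man with no response has a flat curve, so rAUC = C0 × S − C0 × W = C0 × (S − W). The correct value is 0.

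- *Rectangle as wide as the curve* (W = S): the residual is 0 whichever pre-stress sample is T0 and whatever the minutes turn out to be.
- *W = 24, curve from Baseline*: the residual is 53 − 24 = 29, or 46 − 24 = 22, times C0. Over 53 minutes, 29 × 0.17 = 4.93 and 29 × 0.31 = 8.99 μg/dL × min. Over 46 minutes, 22 × 0.17 = 3.74 and 22 × 0.31 = 6.82. The spurious race difference is 29 × 0.14 = 4.06, or 22 × 0.14 = 3.08.
- *W = 24, curve from the pre-TSST sample*: 41 − 24 = 17, or 34 − 24 = 10, times that sample's value.
- *T0 at the end of the TSST*: the curve can start only at the +2-minute sample, so the residual is (22 − 24) = −2 times baseline. A 0.14 gap then gives −0.28.

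**Effect on the race test if W = 24 from Baseline.** This was simulated with 5000 runs, 50 men per group, equal mean responses and a Welch t-test. Baseline distributions, response profile and response SDs (0.1 to 0.3) were all assumed. For assumed baseline gaps of 0.05, 0.10 and 0.14 the false-positive rates were 9–14%, 21–44% and 37–75%. With matched windows they were 4.3–5.7% throughout.

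**Which width does the text describe?** The curve sentence introduces T24m as the name of the last measurement. The next sentence attaches almost the same label to the total observation time and subtracts the rectangle from the total area. Three points follow:

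1. T24 is first used for an endpoint, and the schedule has a sample with that name, 24 minutes after the TSST.
2. The noun that fixes the width is the whole observation time, which is the span of the curve. A 24-minute width against a 46- to 53-minute curve contradicts that noun.
3. The height is the baseline sample, and one row of the schedule is labelled Baseline.

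**The remark on negative values.** It says only that negative values can occur, so it is compatible with either width and contradicts neither. With W = 24, rAUC is negative only when average cortisol falls below 24/53 = 45% or 24/46 = 52% of baseline. With a matched window, any curve whose average lies below baseline is negative, which is the behaviour that the remark more naturally describes.

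**The case for a change.** The strongest case for a change is that the plan prints a number where the formula needs a width, and that the number fits no scheduled starting sample. Intent does not bind a programmer. Even with matched windows, someone must choose between the 3:15 and 3:27 samples, and that choice alters both the baseline value and the window. rAUC is a main Aim 1 outcome, the error could favour the study's hypothesis, and the remedy is one sentence.

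Some of this stands. T0 is not named, the T24min label is loose, and the arithmetic of the literal reading is right. It does not carry the conclusion, for three reasons. Coding 24 means setting aside the words that define the width. Choosing between two pre-stress samples is an ordinary analyst's decision, and the row labelled Baseline points to the answer. Either choice with a matched window gives a proper baseline-corrected area. The sentence proposed would also only write down the analysis that a sensible reader would already run.

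The reach is limited as well. The first-minus-last blunting measure, the timepoint comparisons, craving, smoking after the TSST and the power statements do not use rAUC.

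**Conclusion.** The concern does not call for a change. The schedule arithmetic is correct, but the plan, read in the ordinary way, subtracts a rectangle covering the same window as the curve, and the residual is then zero. The figure of 22 to 29 times baseline (10 to 17 times from the pre-TSST sample) arises only if a label for the last sample is coded as a duration. The larger false-positive rates need, in addition, a racial gap in baseline cortisol that the documents do not report, plus assumed response profiles and SDs. This is a missing definition that an analyst fills from the timeline in Section 8.0. The conclusion rests on T24m and T24min both naming the last sample, which is how Section 10.1 first uses the label.

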5.0 Number of Subjects

The study will enroll 100 African American (n=50) and white (n=50) male smokers.

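### Aim 2's stated 83% power for absolute cortisol does not follow from its own inputs, which give about 63%

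*Combined protocol and SAP*

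**What the plan says.** Section 5.0 fixes the sample: "The study will enroll 100 African American (n=50) and white (n=50) male smokers". Section 10.1 then gives two power statements for Aim 2, both for a two-sided two-sample t-test at 0.05.

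- The first concerns the diurnal cortisol slope (DCS): "A sample size of 50 AA/Black (Mean DCS=0.12, SD=0.15) and 50 white (Mean DCS=0.26, SD=0.30) males achieves 84% power", for a difference of 0.14 μg/dL.
- The second concerns absolute cortisol: "This sample size would also provide 83% power to detect a difference of 0.13" μg/dL "in absolute cortisol value between AA/Black (mean=0.35, SD=0.19) and white (mean=0.48, SD=0.35) males with a significance level of 0.05".

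Lower absolute cortisol over the waking day in African American smokers is one of the two hypotheses named for Aim 2 in Sections 1.0 and 10.1. The second statement is the only power justification given for it.

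**The concern.** The two Aim 2 statements use the same group sizes and the same test. The second has a smaller difference (0.13 against 0.14) and larger SDs in both groups (0.19 against 0.15, and 0.35 against 0.30). Its power should therefore be clearly lower, yet it is stated as 83% against 84%.

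At stake is how well the study can test the absolute-cortisol hypothesis. If the printed SDs are right, the plan presents as adequately powered a comparison that is not, and a reader relying on 83% could take a null result as stronger evidence of no difference than it is.

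**Working it through.** **Inputs**, all from the Aim 2 sample-size paragraph in Section 10.1, with the group size also in Section 5.0:

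- n = 50 per group
- means 0.35 and 0.48, so the difference is 0.13, as stated
- SDs 0.19 (AA/Black) and 0.35 (white)
- two-sided alpha 0.05, two-sample t-test

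**Formula.** SE = √((SD₁² + SD₂²)/n). By the normal approximation, power = Φ(difference/SE − 1.960); the opposite tail is negligible here.

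**Can the plan's other figures be reproduced?** The same formula was applied to all four race comparisons in Aims 1 and 2, each with 50 per group.

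| Comparison | Difference | SDs | SE | Difference/SE | Power, normal | Power, Welch t | Stated |
|---|---|---|---|---|---|---|---|
| Aim 1 DCS | 0.15 | 0.20, 0.30 | 0.0510 | 2.94 | 83.7% | 82.9% | 84% |
| Aim 1 absolute | 0.14 | 0.19, 0.30 | 0.0502 | 2.79 | 79.6% | 78.7% | 80% |
| Aim 2 DCS | 0.14 | 0.15, 0.30 | 0.0474 | 2.95 | 83.9% | 82.9% | 84% |
| Aim 2 absolute | 0.13 | 0.19, 0.35 | 0.0563 | 2.31 | 63.6% | 62.5% | **83%** |

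The first three agree with the plan after rounding under the normal approximation. The fourth does not.

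**The disputed figure in full.**

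- SE = √((0.0361 + 0.1225)/50) = √0.003172 = 0.0563
- 0.13/0.0563 = 2.308
- Normal approximation: Φ(2.308 − 1.960) = Φ(0.348) = 63.6%
- Noncentral t, pooled variance, 98 df: 62.8%
- Noncentral t, Welch, 75.6 df: 62.5%
- Simulation of 200,000 trials: 62.5% (pooled) and 62.2% (Welch)

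**Does another reading give 83%?**

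- One-sided test at 0.05: 74% to 75%; the text says two-sided.
- Arithmetic mean of the two SDs: 66.4%.
- One SD for both groups: 45.2% with 0.35, 92.3% with 0.19.
- Log scale, lognormal with the printed means and SDs: 50%. Using the log ratio of the arithmetic means instead: 76%.
- 100 per group: 90.0%.
- Averaging the 4- and 8-week visits: the variance is multiplied by (1 + ρ)/2, where ρ is the between-visit correlation. The documents give no ρ. Power runs from 89.7% at ρ = 0 to 64.7% at ρ = 0.9 and is near 83% only around ρ = 0.2 (83.7%). At that value the Aim 2 DCS power would be 96%, against the stated 84%.

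**What would make the sentence true?** By the Welch calculation, changing one input at a time:

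- white-group SD of about 0.25 (0.25 gives 82.6%, or 83.3% by the normal approximation);
- or a difference of 0.166 (0.160 for 80% power);
- or about 81 per group (about 75 for 80% power).

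**The case against.** The arithmetic mismatch is not in dispute. The case on the other side concerns what follows from it.

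- **The SD may be the misprint.** With a white-group SD of 0.25, the method that matches the other three figures gives 83.3%, which rounds to the stated value. In that case the power is right and nothing is underpowered. This stands as a possibility, but it is an inference; no passage supports 0.25 over 0.35. It is the reason to check the source before changing the power.
- **The t-test is not the planned analysis.** The Aim 2 analysis is a repeated-measures model with race, time of day and their interaction, fitted separately at 4 and 8 weeks. Its power depends on within-person correlations that the plan does not give. This also stands: 63% is the power of the stated t-test, not of the final model. It does not rescue 83%, because the sentence ties that figure to the t-test.
- **The figure is supplementary.** Section 10.1 names change in cortisol as the Aim 2 primary outcome, and the DCS calculations that support 50 per group reproduce. That limits the consequence: the sample size does not rest on this sentence. The sentence is still the only power claim for a named hypothesis.
- **Over-interpretation of a null result is a prediction.** Fair. It is a risk, since the documents do not say how a null result would be read.

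**Conclusion.** The concern holds. As printed, the inputs and the power for the Aim 2 absolute-cortisol comparison cannot both be right. The inputs give 62.5% to 63.6%, about 20 points below the stated 83%, and no alternative supported by the text closes the gap. The other three race-comparison figures are sound.

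If the SD of 0.35 is correct, the type II error for a true difference of 0.13 under the stated test is about 37% (100 − 63), not 17% (100 − 83). That assumes complete data on all 50 men per group. The power text makes no allowance for men lost before the 4- and 8-week samples; purely for illustration, 45 per group would give 57.9% and 40 per group 52.9%. If the SD was meant to be about 0.25, the power stands and only the SD needs correction.

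**What to change.** Check the white-group SD against its source, then correct the sentence in Section 10.1, Aim 2:

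- If 0.35 is confirmed, state about 63% power for a difference of 0.13 μg/dL, or equivalently 80% power for a difference of about 0.16 μg/dL, with 50 per group.
- If 0.25 was intended, correct the SD and keep 83%.
- If the source gives another value, recompute the power from it.

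The cost is one sentence. In the first case a stated figure becomes less favourable. No extra participants, procedures or changes to the analysis model are needed.
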